#### 5.1.1 Inclusion criteria

- 1) Patients aged 20 years or older (at the time of signing informed consent)
- 2) Patients providing written informed consent for study participation in person

---

- 3) Patients with chronic renal failure on periodic hemodialysis (HD, off-line HDF, on-line HDF, or I-HDF) 3 times weekly for  $\geq 12$  weeks prior to the informed consent procedure (including the date of informed consent) who can continue hemodialysis without changing its frequency or method (any temporary change in dialysis frequency or method associated with travel or admission to other hospitals with no changes in treatment strategies is acceptable) from the date of informed consent until the end of the follow-up period
- 4) Patients whose pruritus treatment within 1 year prior to the informed consent procedure meets either (1) or (2) below:
  - (1) Drug therapy with nalfurafine hydrochloride for  $\geq 2$  consecutive weeks
  - (2) Inadequate response to both drug therapies a) and b) below:
    - a) Systemic (e.g., oral, injection) therapy with antihistamines or antiallergics contained in prescription drugs indicated for the treatment of itching for  $\geq 2$  consecutive weeks
    - b) Local (topical) therapy with prescription drugs indicated for the treatment of itching or moisturizers prescribed by physicians
- 5) Patients whose pruritus has been treated with 1 or more drugs listed below since prior to the start of the screening period:
  - Drugs indicated for the treatment of itching (prescription/nonprescription) (excluding nalfurafine hydrochloride)
  - Drugs to treat itching (prescription/nonprescription)
  - Moisturizing drugs (prescription/nonprescription)
  - Products formulated with any of the above
- 6) Patients whose NRS score in the 7 days prior to the start of the double-blind period (7 days including the score recorded on the start day of treatment) ([Appendix 1](#)) meets both of the below:
  - NRS scores have been recorded for  $\geq 5$  days.
  - The mean value of the recorded scores exceeds 4.0 (not including 4.0).
- 7) Patients whose itch score based on the Shiratori's severity criteria ([Appendix 2](#)) in the 7 days prior to the start of the double-blind period (7 days including the score recorded on the start day of treatment) meets both of the below:
  - Itch scores during the day and the night have been recorded for  $\geq 5$  days.

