### 8.6.2 Rationale for the sample size

#### 8.6.2.1 Double-blind period

In a Japanese phase II clinical study (MR13A9-4), the change from baseline in the mean NRS score at Week 4 of the treatment period (mean  $\pm$  standard deviation) was  $-2.15 \pm 1.98$  in the placebo group and  $-3.22 \pm 2.09$  in the MR13A9 0.5 µg/kg group. The difference for the MR13A9 0.5 µg/kg group versus the placebo group at Week 4 of the treatment period was  $-1.04 \pm 0.35$  (adjusted mean  $\pm$  standard error).

For the primary variable of change from baseline in the mean NRS score at Week 4 of the double-blind period, its mean difference for the MR13A9 0.5 µg/kg group versus the placebo group was assumed to be  $-1.0$ , with a common standard deviation of  $2.0$ . Assuming a two-sided significance level of  $5\%$  and a statistical power of  $90\%$ , the sample size required to confirm the superiority of the MR13A9 0.5 µg/kg group to the placebo group using a two-sample t-test was calculated to be 86 subjects per group.

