6.5.3 Multiplicity of multiple analysis sets

For the double-blind period, the FAS will be used as the primary analysis set for efficacy, and the PPS will be used for the supplemental analysis to examine the robustness of the results, so multiplicity among multiple analysis sets will not be adjusted. It is not applicable for safety because only the SS is used as the analysis set.

For the entire study period, it is not applicable for efficacy because only the FAS is used as the analysis set. It is not applicable for safety because only the SS is used as the analysis set.

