6.8 Examination of Subgroups

As the subgroup analyses of efficacy endpoints, the matters shown in “[11.3 Efficacy Subgroups](#)” will be performed. As the subgroup analyses of safety endpoints, the matters shown in “[12.5 Safety Subgroups](#)” will be performed.

7. Definition of Derived Data

Each variable will be calculated using the following formula:

- Disease duration of itch (years) = Date of written informed consent (year) – Time of onset of itching (year)
- Hemodialysis history (years) = Date of written informed consent (year) – Date of initiation of hemodialysis (year)
- Urea reduction ratio at baseline (%) = $([\text{BUN before dialysis} - \text{BUN after dialysis}] / \text{BUN before dialysis}) \times 100$

- Treatment compliance (%) = Number of doses of the study drug / Number of dialysis sessions performed during the double-blind and extension periods $\times 100$
- Treatment duration (days) = Day of the final dose – Start of the study treatment + 1
- Average dose per dry weight ($\mu\text{g}/\text{kg}$) = Total dose of the study drug per dry weight / Number of doses
- NRS score and itch score based on Shiratori's severity criteria
 - Mean score at each time point = Sum of scores observed during the assessment time window / Number of days when the score was observed during the assessment time window
 - *The details of the assessment time window are shown in [Table 11.1-1](#) and [Table 11.1-2](#).
 - Change from baseline in the mean score at each time point = Mean score at each time point – Mean score at baseline
 - Change from baseline in daily score = Daily score – Mean score at baseline
- Skindex-16¹⁾
 - Score for each question = Response for each question / 6 $\times 100$
 - Total score = Sum of scores for all questions / 16
 - Subscores
 - Symptoms score = (Sum of scores for Questions 1 to 4) / 4
 - Emotions score = (Sum of scores for Questions 5 to 11) / 7
 - Functioning score = (Sum of scores for Questions 12 to 16) / 5
- 5-D itch scale
 - The total score will be calculated as the sum of scores for the following questions (components)²⁾:
 - (1) Duration: 1 to 5 points
 - (2) Degree: 1 to 5 points
 - (3) Direction: 1 to 5 points
 - (4) Disability: 1 to 5 points
 - The highest score among sleep, leisure/social, housework/errands, and work/school will be used.
 - (5) Distribution: 1 to 5 points
 - The score is determined according to the total number of body parts with itching as follows:
 - 0 to 2: 1 point
 - 3 to 5: 2 points

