11.1.1.1 Primary analysis

Using the data obtained up to Week 4 of the double-blind period, the superiority of the MR13A9 0.5 µg/kg group to the placebo group will be confirmed by performing the analysis using a mixed-effects model for repeated measures (MMRM) with change from baseline in the mean NRS score at each time point as an objective variable; treatment group, time point, and treatment group-by-time point interaction as fixed effects; baseline mean NRS score and the

presence or absence of prior treatment with nalfurafine hydrochloride as a dynamic allocation factor as a covariate; and subject as a random effect.

The analysis will include all available data obtained at each time point from Week 1 to Week 4 of the double-blind period as objective variables. Estimation will be performed using a restricted maximum likelihood method. An unstructured covariance structure will be used to estimate error variance. If the unstructured covariance structure fails to provide convergence, the structure that minimizes Akaike Information Criterion (AIC), among the Toeplitz, first-order autoregressive, and compound symmetry structures, will be used. The degree of freedom will be adjusted with the Kenward-Roger method.

The number of subjects, adjusted mean of the change, standard error, and two-sided 95% confidence interval in each group at each time point will be presented, and the adjusted mean and standard error will be presented in graphs. The adjusted mean between-group difference in the change at each time point for the placebo group and the MR13A9 0.5 µg/kg groups and its two-sided 95% confidence interval as well as the P value will be presented.

The assessment time points are Weeks 1 to 4.

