11.3 Efficacy Subgroups

The same analyses as described in “[11.1.1.1 Primary analysis](#)” and “[11.1.2 Other assessment variables](#)” will be performed on data from the double-blind period in each of the subgroups defined by prior treatment with nalfurafine hydrochloride (no, yes) and mean NRS score at baseline (< 6, ≥ 6). For the subgroup defined by prior treatment with nalfurafine hydrochloride, only the mean NRS score at baseline will be used as a covariate in the model.

12. Safety

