- (7) In “11.1.2.4 Change from baseline in the daily NRS score” and “11.2.1.3 Change from baseline in daily itch score,” the text has been updated to include MMRM analysis as performed in the primary analysis.
Reason: To perform an analysis that takes into account the influence of covariates and correlations between time points.
- (8) In “11.2.3 5-D Itch Scale,” component scores (duration, degree, direction, disability, and distribution scores) have been added to the analysis items.
Reason: To perform a more detailed evaluation of the 5-D Itch Scale data.
- (9) In “11.2.2.1 Changes from baseline in Skindex-16” and “11.2.3.1 Changes from baseline in 5-D itch scale,” the variables to be displayed for analysis of covariance have been described.
Reason: To clarify the variables to be displayed.
- (10) In “11.3 Efficacy Subgroups,” the same analysis as described in “11.1.2 Other assessment variables” has been added.
Reason: To perform a more detailed evaluation of the NRS score in subgroups.
- (11) In “11.3 Efficacy Subgroups,” a subgroup defined by the mean NRS score at baseline

(< 6 , ≥ 6) has been added.

Reason: To evaluate whether efficacy varies depending on the mean baseline NRS score.

(12) In “12.1.6 Details of adverse events of special interest,” “adverse events of special interest occurring between the start of study treatment and the end of the extension period” has been added to the events to be tabulated in the entire study period.

Reason: To perform a more detailed evaluation of adverse events of special interest.

(13) In “12.4.1 Evaluation of dependency based on judgment by dependency assessment members,” the description of the target assessments (interim and final) has been added.

Reason: To clarify the target assessments.

3) Changes in the statistical analysis plan version 3.0

(1) “11.2.1.5 Percentage of subjects with improvement in night-time mean itch score” has been added.

Reason: To evaluate in more detail of the improvement in night-time itching.

16. History of Revision of Statistical Analysis Plan

Version	Date of creation/revision	Author	Description
1.0	January 7, 2021	[name]	First version prepared
2.0	November 16, 2021	[name]	Revised version prepared
3.0	October 24, 2022	[name]	Revised version prepared

17. Literature References

- 1) Higaki Y. Skindex-16 (Japanese version): A skin disease-specific quality of life scale. Tokyo. Medical Professional Relations Inc. 2002.

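### SAP 11.3 adds a baseline-NRS subgroup to see whether efficacy varies, but plans no estimate or CI of the difference between the two subgroup effects

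*SAP*

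**What the plan says.** SAP 11.3 runs the primary analysis and the other NRS analyses on double-blind data "in each of the subgroups defined by prior treatment with nalfurafine hydrochloride (no, yes) and mean NRS score at baseline", the NRS cut being <6 and ≥6. The model that is repeated (SAP 11.1.1.1) has "treatment group, time point, and treatment group-by-time point interaction as fixed effects". For each time point it reports the adjusted drug–placebo difference, and "its two-sided 95% confidence interval as well as the P value will be presented". Section 11.3 therefore yields one such set for baseline NRS <6 and another for ≥6.

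The reason for the baseline-NRS split is in SAP 15, changes in version 2.0, item (11): "To evaluate whether efficacy varies depending on the mean baseline NRS score". No purpose is given for the prior-nalfurafine split, so this point is limited to baseline NRS.

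Nothing elsewhere fills the gap. SAP 6.8 ("As the subgroup analyses of efficacy endpoints, the matters shown in" section 11.3) is only a cross-reference. SAP 6.1 deals with covariates and plans no treatment-by-baseline term. Protocol section 14 has no efficacy subgroup analysis.

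**The concern.** Whether efficacy varies with baseline NRS is a question about one quantity: the treatment effect in the ≥6 level minus the effect in the <6 level. The plan produces the two ingredients but not the quantity or its uncertainty. The only interaction in the repeated model is treatment-by-time, which says nothing about baseline severity.

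With two separate results on the page, the easy comparison is between the two P values, and that comparison misleads. When each level has only moderate power, one significant and one non-significant result is a common outcome even if the drug works equally well in both. What is at stake is how this subgroup table is read, not the primary result.

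**Working it through.** **Inputs.** From protocol 8.6.2.1: difference −1.0, common SD 2.0, two-sided 5%, 90% power, and a sample size that "using a two-sample t-test was calculated to be 86 subjects per group". Allocation is 1:1 (protocol 8.5.3.5). The documents do not give the share of subjects below 6, so splits from 50:50 to 80:20 are assumed, the same in both arms. Covariate gains and missing data are ignored.

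**Step 1: reproduce the design.** With n = 86, SE = 2.0 × √(2/86) = 0.305, and the noncentrality is 1.0/0.305 = 3.28 on 170 df. Exact t power is 0.903, against 0.8999 at n = 85. The stated 86 per group is reproduced.

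**Step 2: power within each level.** The same formula is used with n per arm in the level. Let p and q be the two powers when the true effect is −1.0 in both levels.

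**Step 3: discordance.** The levels contain different subjects, so P(exactly one significant) = p(1 − q) + q(1 − p). At 43/43 this is 2 × 0.630 × 0.370 = 0.466. The last column is from a simulation with a uniform effect: how often the direct contrast is significant among the discordant trials.

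| n per arm in the two levels | p, q | Exactly one significant | Contrast significant, given discordance |
|---|---|---|---|
| 43 / 43 (50:50) | 0.630, 0.630 | 0.466 | 0.101 |
| 52 / 34 (60:40) | 0.714, 0.529 | 0.488 | 0.095 |
| 60 / 26 (70:30) | 0.775, 0.424 | 0.542 | 0.079 |
| 69 / 17 (80:20) | 0.830, 0.293 | 0.637 | 0.059 |

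**Step 4: precision of the contrast.** SE = 2.0 × √(2/n₁ + 2/n₂), and the half-width is t(0.975, 168 df) × SE. At 43/43, SE = 2.0 × √(4/43) = 0.610, and 1.974 × 0.610 = 1.20.

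| Split | SE | 95% CI half-width | Power for a 1.0-point difference in effect | Difference detectable with 80% power |
|---|---|---|---|---|
| 50:50 | 0.610 | 1.20 | 0.371 | 1.72 |
| 70:30 | 0.664 | 1.31 | 0.322 | 1.87 |
| 80:20 | 0.766 | 1.51 | 0.255 | 2.16 |

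**Step 5: unequal SDs.** A common SD is doubtful here. Inclusion criterion 6 (protocol 5.1.1) requires a baseline mean above 4.0, so the <6 level spans less than 2 points at baseline and cannot improve by 6 points or more. SDs of 1.6 (<6) and 2.2 (≥6) are assumed for illustration; the documents give no SD by baseline level. Discordance is then 0.461 at 30:70 (<6 : ≥6), 0.469 at 50:50 and 0.617 at 70:30.

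This also bears on how the contrast is computed. With these SDs and no true difference between levels, a single pooled variance gives a type I error of 0.027 at 26/60 per arm and 0.084 at 60/26. Separate standard errors with Satterthwaite df give 0.050 in both. At 69/17 with SD 2.0 throughout, separate standard errors referred to the normal distribution give 0.055, and Satterthwaite df give 0.050.

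**The case against.** The best defence is that the contrast is nearly in the output already. The two levels share no subjects, each gets an estimate and a 95% CI, and the difference and its approximate SE follow by hand. What is missing is one derived line. This stands, and it is the main reason the point is minor.

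The SAP also states no rule of comparing the two P values, so the discordance figures measure the scope for misreading and are not an error rate of the plan. That is correct, and they should be read that way.

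Third, SAP 6.5.2 treats everything other than the primary variable as reference, no claim rests on the subgroup, and the stated purpose is a single reason line that a descriptive side-by-side display might be said to meet. The low weight is accepted. But a side-by-side display still leaves the reader to form the comparison that the line names as the purpose.

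Fourth, the added line would usually be inconclusive: its half-width exceeds the whole design effect of 1.0. This is true, but an interval that wide tells the reader directly how little can be said, which two separate P values do not.

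The table shells are provided separately (SAP 14) and were not available, so a display of the contrast cannot be ruled out. The SAP text does not specify one.

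**Conclusion.** The point holds and is minor. The subgroup was added to answer a question about effect variation, and the planned analyses stop short of the quantity that answers it. Under a uniform effect of −1.0, the two levels would disagree on significance in about 46% to 64% of trials over the splits and SDs tried. With SD 2.0, the direct contrast would be significant in only about 6% to 10% of the discordant ones. The contrast would carry a CI of about ±1.2 to ±1.5 points and 25% to 37% power for a 1.0-point difference in effect.

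These sizes rest on assumed splits and, in Step 5, assumed SDs; they show a range and do not predict this trial's result. The omission itself does not depend on them. The primary conclusion is untouched: "the FAS will be used as the primary analysis set for efficacy", with Week 4 as the primary time point.

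**What to change.** Add one sentence to SAP 11.3: as an exploratory analysis, report the Week 4 difference between the baseline-NRS <6 and ≥6 treatment effects with its two-sided 95% CI. Compute it from the two separately fitted MMRMs, with SE = √(SE₁² + SE₂²) and df = (SE₁² + SE₂²)² / (SE₁⁴/df₁ + SE₂⁴/df₂). A single interaction MMRM is equivalent if covariance and covariate slopes may differ by subgroup. A model with one shared covariance should be avoided, for the reason in Step 5.

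State alongside it that precision is low and that a non-significant difference is not evidence of a uniform effect. Keep the within-level results.

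Two optional additions are a treatment-by-continuous-baseline-by-time estimate at Week 4 with its CI, and the same contrast for prior nalfurafine as a consistency check.

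The documents do not say when the double-blind data were locked. If they are already unblinded, label the contrast post hoc.

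The cost is one sentence and one imprecise line in the subgroup table. The main option needs no new model and no new data, and the primary analysis does not change.

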12.1 Adverse Events and Adverse Drug Reactions

Unless otherwise specified, the following events will be tabulated.

- Double-blind period
 - Events occurring between the start of study treatment and the end of the double-blind period
 - Adverse events of special interest occurring between the start of study treatment and the end of the double-blind period
- Entire study period
 - Events occurring between the start of study treatment and the end of the follow-up period

- Events occurring between the start of study treatment and the end of the extension period
- Adverse events of special interest occurring between the start of study treatment and the end of the follow-up period
- Adverse events of special interest occurring between the start of study treatment and the end of the extension period

12.1.1 Incidence of adverse events and adverse drug reactions

The number of events, the number of subjects experiencing events, the incidence of events and its two-sided 95% confidence interval will be presented. For the double-blind period, a Fisher's exact test will be used for comparisons between the placebo group and the MR13A9 0.5 µg/kg group. The difference in the incidence between the placebo group and the MR13A9 0.5 µg/kg groups and its two-sided 95% confidence interval will be presented.

12.1.2 Incidences of adverse events and adverse drug reactions (serious adverse events, adverse events leading to interruption/discontinuation of treatment, and adverse events of special interest)

The events to be tabulated are as follows.

- Double-blind period: Events occurring between the start of study treatment and the end of the double-blind period
- Entire study period
 - Events occurring between the start of study treatment and the end of the follow-up period
 - Events occurring between the start of study treatment and the end of the extension period

The number of events, the number of subjects experiencing events, and the incidence of events will be presented for all events, events leading to death, serious events other than death, events leading to interruption, and events leading to discontinuation.

12.1.3 Occurrence of adverse events and adverse drug reactions

The number of subjects experiencing events and the incidence of events will be presented for all events and by primary SOC and PT.

12.1.4 Occurrence of adverse events and adverse drug reactions (by severity)

The numbers of events by severity will be presented for all events and by primary SOC and PT.

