### 1.3.2.2 Efficacy and safety

In a Japanese phase II clinical study (MR13A9-3), 105 previously treated hemodialysis patients with pruritus received MR13A9 0.25, 0.5, 1.0, or 1.5  $\mu$ g/kg, or placebo injected into the venous line of the dialysis circuit at the end of each dialysis session 3 times weekly for 2 weeks. The primary endpoint of change in VAS (i.e., change based on the larger VAS value either in the morning or the evening during the 7 days, the latter half of the treatment period) suggested a dose-dependent improvement by treatment with MR13A9 at doses  $\geq 0.5$   $\mu$ g/kg. Common adverse drug reactions (reported in  $\geq 10\%$  of subjects in any of the MR13A9 groups) included blood thyroid stimulating hormone decreased, dizziness, blood prolactin increased, nausea, feeling abnormal, and somnolence. Study treatment was discontinued or interrupted due to 1 event in 1 subject in the 0.25  $\mu$ g/kg group, 2 events in 2 subjects in the 0.5  $\mu$ g/kg group, 1 event in 1 subject in the 1.0  $\mu$ g/kg group, and 17 events in 10 subjects in the 1.5  $\mu$ g/kg group. Dependency was assessed as being present in 2 subjects in the placebo group and 1 subject in the MR13A9 0.5  $\mu$ g/kg group.

In a Japanese phase II clinical study (MR13A9-4), 247 previously treated hemodialysis patients with pruritus received MR13A9 0.25, 0.5, or 1.0  $\mu$ g/kg, or placebo injected into the venous line of the dialysis circuit at the end of each dialysis session 3 times weekly for 8 weeks. The primary variable of change from baseline in the mean NRS score at Week 8 of the treatment period (adjusted mean  $\pm$  standard error) was  $-2.97 \pm 0.29$  in the MR13A9 0.25  $\mu$ g/kg group,  $-3.65 \pm 0.30$  in the 0.5  $\mu$ g/kg group, and  $-3.64 \pm 0.30$  in the 1.0  $\mu$ g/kg group, compared with  $-2.86 \pm 0.29$  in the placebo group. These results showed significant

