### 10.13.3 Severity of adverse events

The severity of adverse events will be categorized into 3 grades according to [Table 10.13.3-1](#). For an adverse event in which the severity changes, the highest severity will be recorded.

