12.1.6 Details of adverse events of special interest

The events to be tabulated are as follows.

- Double-blind period: Adverse events of special interest occurring between the start of study treatment and the end of the double-blind period
- Entire study period
 - Adverse events of special interest occurring between the start of study treatment and the end of the follow-up period
 - Adverse events of special interest occurring between the start of study treatment and the end of the extension period

The number of events, the number of subjects experiencing events, and incidence of adverse events and adverse drug reactions will be presented. The number of events will be presented by severity (mild, moderate, or severe), action taken with study treatment (drug withdrawn, drug interrupted, dose not changed, unknown, or not applicable), outcome (recovered/resolved, recovering/resolving, not recovered/not resolved, recovered/resolved with sequelae, results in death, or unknown), and time of resolution (during the double-blind period, during the extension period, or after entering the follow-up period).

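### Adverse event severity is tabulated only as numbers of events, so no described table gives the number or percentage of subjects with a moderate or severe event

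*SAP*

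**What the plan says.** SAP 12.1.4 deals with the severity of all adverse events and adverse drug reactions in one sentence: "The numbers of events by severity will be presented for all events and by primary SOC and PT". Protocol 14.6.1 item 4) uses the same sentence.

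For adverse events of special interest, SAP 12.1.6 gives events, subjects and incidence in total, but its breakdown counts events only: "The number of events will be presented by severity (mild, moderate, or severe), action taken with study treatment", followed by outcome and time of resolution.

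The neighbouring table with the same SOC and PT rows uses subjects: "The number of subjects experiencing events and the incidence of events will be presented for all events and by primary SOC and PT" (SAP 12.1.3). The overall table in SAP 12.1.1 gives both units: "The number of events, the number of subjects experiencing events, the incidence of events and its two-sided 95% confidence interval will be presented". The between-group test also sits there: "For the double-blind period, a Fisher's exact test will be used for comparisons between the placebo group and the MR13A9 0.5 µg/kg group". Neither table is split by severity.

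Protocol 10.13.3 sets three grades and a rule within a single event: "For an adverse event in which the severity changes, the highest severity will be recorded". Neither document defines a highest grade per subject.

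**The concern.** The usual question about severity is how many patients in each group had a moderate or severe reaction. A count of events does not answer it, because it has no subject numerator and no denominator, and several events may belong to one person.

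Repeats are possible in this trial. Dosing is three times weekly, and Protocol 10.13.5 has the investigator ask every week about the symptoms in Appendix 4, which include dizziness and somnolence, and decide each time whether one is an adverse event. Safety is a secondary objective (Protocol 3.2), and Protocol 4.2.2 singles out central nervous system effects for careful assessment. A severity profile that cannot be turned into a proportion of patients is of limited use for either purpose.

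**Working it through.** **1. Every safety output described, by unit and severity split**

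| Output | Counts subjects? | Split by severity? |
|---|---|---|
| SAP 12.1.1, overall incidence | Yes | No |
| SAP 12.1.2, death, other serious, interruption, discontinuation | Yes | No |
| SAP 12.1.3, by SOC and PT | Yes | No |
| SAP 12.1.4 and Protocol 14.6.1 item 4) | No | Yes |
| SAP 12.1.5, by time of onset | Yes | No |
| SAP 12.1.6, special interest, totals | Yes | No |
| SAP 12.1.6, special interest, severity line | No | Yes |
| SAP 12.5, subgroups | Yes | No |

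No row has a yes in both columns. The by-subject listings in SAP 12.6 have no category for moderate or severe events. SAP 12.4.1 does report a severity as number and percentage of subjects, but this is the severity of dependency, not of adverse events.

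**2. Denominator**

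The documents give no counts by severity, so the planned size is used: 86 per group (Protocol 8.6.1). It reproduces. With a difference of 1.0, SD 2.0, two-sided 5% and 90% power, n = 2 × (1.960 + 1.282)² × 2.0² / 1.0² ≈ 84.1, that is 85 by normal approximation. The two-sample t-test gives 85.03, rounded up to 86.

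**3. One severity table, two different patient risks (assumed counts)**

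Suppose the MR13A9 group has 6 moderate or severe events and the placebo group has 3, the latter in three subjects.

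- All 6 in one subject: 1/86 = 1.2% against 3/86 = 3.5%.
- The 6 in six subjects: 6/86 = 7.0% against 3/86 = 3.5%.

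SAP 12.1.4 would print 6 and 3 in both cases, an apparent two-fold excess, although the direction per patient is reversed in the first. Neither contrast is near significance (Fisher p = 0.62 and 0.50). The point is the size and direction of a descriptive figure, not a missed test.

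**4. Can the other tables recover the number?**

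Let S be the subjects with a given PT (SAP 12.1.3), and m the moderate or severe events and e the mild events for that PT (SAP 12.1.4). Let X be the unknown number of subjects with at least one moderate or severe event. X cannot exceed S or m. Subjects outside X each need at least one mild event, so S − X ≤ e. With m at least 1:

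max(1, S − e) ≤ X ≤ min(S, m)

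Example (assumed): S = 5, m = 3, and at least 5 − 1 = 4 mild events. Then X may be 1, 2 or 3, that is 1/86 = 1.2%, 2/86 = 2.3% or 3/86 = 3.5%. The tables bound X and identify it only in special cases. For all PTs together the gap remains, because PT rows cannot be summed without counting some subjects twice.

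**5. How recurrence enters (assumed counts)**

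Suppose 8 subjects per arm have a moderate event, 8/86 = 9.3% in both. If one MR13A9 subject has it recorded as a new event at each of six weekly interviews, the event counts are 7 + 6 = 13 against 8, a ratio of 1.6 with equal subject proportions. This needs each recurrence to be recorded separately. The documents do not say whether a symptom that returns after a later dose is a new event.

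**The case against.** The strongest reply is that little depends on this table. Severity is descriptive. The tested comparison of adverse events and its confidence interval (SAP 12.1.1) count subjects. Deaths, other serious events, and events leading to interruption or discontinuation are counted by subject with incidence (SAP 12.1.2) and by onset category (SAP 12.1.5). Clustering in a special-interest symptom may be visible anyway: if the eight subjects in step 5 were all the cases of that PT, SAP 12.1.3 would show 8/86 in each arm, and SAP 12.6 lists special-interest events by subject. Severity is recorded for each event after treatment starts (Protocol 10.13.1), so the table could be derived later. The table shells are separate and may already include it.

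Most of this stands, and it limits the point to reporting. It does not supply the missing count. Serious is not the same as severe: Protocol 10.13.3 grades interference with daily life and treatment needed, while 10.13.4 turns on outcomes such as death or hospitalisation. A severe but non-serious event that does not interrupt or end treatment has no subject count by grade. Where grades are mixed within a PT, step 4 shows that the subject table does not resolve the matter. Neither document gives a reason for a different unit from SAP 12.1.3.

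**Conclusion.** The plan as written does not yield the number or percentage of subjects with a moderate or severe adverse event, overall, by SOC or PT, or among special-interest events. The size of any distortion cannot be stated from the documents. The figures in steps 3 to 5 rest on assumed counts, and step 5 also on recurrences being recorded separately. The conclusion covers tables described in the Protocol and SAP, not the unseen shells. This is a worthwhile reporting correction that touches no efficacy conclusion and no planned test.

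Four stronger readings are not supported:

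- A reader might infer that one subject could drive the randomised safety comparison. The only planned between-group test of adverse events counts each subject once.
- A reader might take "17 events in 10 subjects" in Protocol 1.3.2.2 as evidence of repeated reactions. That figure is from the 1.5 µg/kg group, a dose not used here. It counts events leading to discontinuation or interruption, which may be different events in one person. At 0.5 µg/kg the same study had 2 events in 2 subjects.
- A reader might treat 18 + 156 = 174 doses as a maximum. It is the scheduled number: an extra fourth weekly session is also dosed, and SAP 10.1 has a category of 181 or more.
- A reader might expect subject counts to make groups with different exposure comparable. Cumulative subject incidence also rises with exposure, so the fix does not achieve that.

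**What to change.** In SAP 12.1.4 and Protocol 14.6.1 item 4), add the number and percentage of subjects by highest severity. Count each subject once at the worst grade: across all events in the overall row, within each SOC in the SOC rows, and within each PT in the PT rows. Use the safety set of each analysis group as denominator and keep the event counts in a second column. Make the same addition to the severity line of SAP 12.1.6. Check the table shells; if they already show this, only the text needs aligning.

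The cost is a few lines of wording and revised shells for the affected tables. No new data are needed, and sample size, significance level and power do not change. The only downside is a wider table. SAP versions 2.0 and 3.0 already added outputs in this way (SAP section 15).
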